### **7.2.1 Definition of an Overdose for This Protocol and Reporting of Overdose to the Sponsor**

Administration of more than 1 dose (> 0.75 mL) of any individual study vaccine in any 24 hour period will be considered an overdose for this protocol.

If an adverse event(s) is associated with (“results from”) the overdose of Sponsor's product or vaccine, the adverse event(s) is reported as a serious adverse event, even if no other seriousness criteria are met.

If a dose of Sponsor's product or vaccine meeting the protocol definition of overdose is taken without any associated clinical symptoms or abnormal laboratory results, the overdose is reported as a non-serious Event of Clinical Interest (ECI), using the terminology “accidental or intentional overdose without adverse effect.”

All reports of overdose with and without an adverse event must be reported within 24 hours to the Sponsor either by electronic media or paper. Sponsor Contact information can be found in the Investigator Trial File Binder.

### **7.2.2 Immediate Reporting of Adverse Events to the Sponsor**

#### **7.2.2.1 Serious Adverse Events**

A serious adverse event is any adverse event occurring at any dose or during any use of Sponsor's product that:

- Results in death;
- Is life threatening;
- Results in persistent or significant disability/incapacity;
- Results in or prolongs an existing inpatient hospitalization;
- Is a congenital anomaly/birth defect;
- Is a cancer;
- Is associated with an overdose;
- Is an other important medical event

Refer to [Table 2](#) for additional details regarding each of the above criteria.

Any serious adverse event, or follow up to a serious adverse event, including death due to any cause, that occurs to any subject from the time the consent is signed through 14 days (42 days for live attenuated vaccines) following the first vaccination(s) and from the time of any subsequent vaccination(s) through 14 days (42 days for live attenuated vaccines) thereafter, whether or not related to the Sponsor's product, must be reported within 24 hours to the

Sponsor either by electronic media or paper. Sponsor Contact information can be found in the Investigator Trial File Binder.

Additionally, any serious adverse event brought to the attention of an investigator who is a qualified physician at any time outside of the time period specified in the previous paragraph also must be reported immediately to the Sponsor if the event is either:

1. A death that resulted in the subject discontinuing the trial  
or
2. A serious adverse event that is considered by an investigator who is a qualified physician to be vaccine related.

All subjects with serious adverse events must be followed up for outcome.

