## 6.0 TRIAL FLOW CHART

Visit Number:	1	2	3	4	5	6	7	8	9
Scheduled Day/Month.:	Day 1	Month 2	Month 6	Month 7	Month 12	Month 18	Month 24	Month 30	Month 36
Visit Window  :		2 months after Day 1, ±3 weeks	6 months after Day 1, ±4 weeks	3 to 7 weeks after Month 6	12, 18, 24, 30 or 36 months after Day 1, ±4 weeks				
Administrative Procedures									
Informed Consent	X								
Informed Consent for Future Biomedical Research	X								
Inclusion/Exclusion Criteria	X								
Subject Identification Card	X								
Medical History	X								
Update Medical History (New condition not already recorded as medical history or adverse experiences)		X	X	X	X	X	X	X	X
Sexual History	X	X	X	X	X	X	X	X	X
Concomitant Medication Review 	X	X	X	X	X	X	X	X	X
Vaccine Allocation/Randomization	X								
V501 /Placebo Administration	X	X	X						
Clinical Procedures/Assessments									
Anogenital Physical Examination	X								
Vital Signs (height, weight, oral temperature, sitting pulse, blood pressure and respiration) 	X	X	X						
Provide Vaccination Report Card (VRC)	X	X	X						
Review and Collect VRC data		X	X	X					
Adverse Events Monitoring	X	X	X	X	X	X	X	X	X
Laboratory Procedures/Assessments									
Genitourinary examination for external genital lesions	X			X	X	X	X	X	X
Penile/glans penis file and wetted swab for HPV PCR 	X			X	X	X	X	X	X
Scrotal file and wetted swab for HPV PCR 	X			X	X	X	X	X	X
Perianal examination for external genital lesions	X			X	X	X	X	X	X
Perineal/perianal file and wetted swab for HPV	X			X	X	X	X	X	X

Visit Number:	1	2	3	4	5	6	7	8	9
Scheduled Day/Month:	Day 1	Month 2	Month 6	Month 7	Month 12	Month 18	Month 24	Month 30	Month 36
Visit Window  :		2 months after Day 1, ±3 weeks	6 months after Day 1, ±4 weeks	3 to 7 weeks after Month 6	12, 18, 24, 30 or 36 months after Day 1, ±4 weeks				
PCR 									
Intra-anal wetted swab for HPV PCR 	X			X	X	X	X	X	X
External genital lesion biopsy (if indicated) 		X	X	X	X	X	X	X	X
Serum for Anti-HPV 	X			X					X
STI Testing (local laboratory testing, if clinically indicated) 	X	X	X	X	X	X	X	X	X
Blood (DNA) for Future Biomedical Research 	X								

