#### **7.1.3.3 External Genital Lesion Biopsy**

After a thorough examination, the investigator's clinical impression should be recorded. If a lesion, in the investigator's opinion, is possibly, probably, or definitely HPV infection-related or the diagnosis is unknown, it should be biopsied for further evaluation. For multiple lesions, select one external lesion to biopsy that is most representative of the morphology or anatomic location, and is most accessible. A second biopsy is indicated, if a lesion is identified in a separate region (anterior region includes penis and scrotum and posterior region includes perineal and perianal region) or a lesion is identified with different morphology in the same region. For each biopsy, different instruments are to be used to prevent cross-contamination

between specimens. At the investigator's discretion, the lesion(s) may be surgically removed (therapeutic excision). In that case, the entire specimen must be submitted for analysis. All specimen(s) excised should be submitted to the central laboratory designated by the SPONSOR for analysis. For the genital wart/lesion biopsy, the external genital lesion biopsy kit provided by the SPONSOR central laboratory is to be used. Slides of the wart/lesion biopsy will be reviewed by a pathologist for the purpose of management of the subject. Management of anogenital warts is a study procedure, but the decision regarding the modality of therapy will be left to the discretion of the investigator, per the site's standard and practices. Excision of the wart/lesion is the preferred study treatment. All excised tissue is to be submitted to the central laboratory for analysis. If more than one biopsy is performed, then use separate instruments for each biopsy. Each biopsy should be placed in individual formalin containers. Treatment of anogenital warts by topical medications or cryotherapy is an acceptable study procedure. A biopsy of the identified lesion/lesions (e.g., morphology differs among identified lesions or more than one lesion is identified) must be obtained prior to administering treatment.

- The investigator should provide a clinical impression of the lesion, which should include one of the following: condyloma acuminata, other HPV-related lesion (e.g., Bowenoid papulosis, Bowen's disease), or other non-HPV related lesions.

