## **7.2 Assessing and Recording Adverse Events**

An adverse event is defined as any untoward medical occurrence in a patient or clinical investigation subject administered a pharmaceutical product and which does not necessarily have to have a causal relationship with this treatment. An adverse event can therefore be any unfavourable and unintended sign (including an abnormal laboratory finding, for example), symptom, or disease temporally associated with the use of a medicinal product or protocol-specified procedure, whether or not considered related to the medicinal product or protocol-specified procedure. Any worsening (i.e., any clinically significant adverse change in frequency and/or intensity) of a preexisting condition that is temporally associated with the use of the Sponsor's product, is also an adverse event.

Changes resulting from normal growth and development that do not vary significantly in frequency or severity from expected levels are not to be considered adverse events. Examples of this may include, but are not limited to, teething, typical crying in infants and children and onset of menses or menopause occurring at a physiologically appropriate time.

Sponsor's product includes any pharmaceutical product, biological product, device, diagnostic agent or protocol-specified procedure, whether investigational (including placebo or active comparator medication) or marketed, manufactured by, licensed by, provided by or distributed by the Sponsor for human use.

Adverse events may occur during the course of the use of the Sponsor's product in clinical trials or within the follow-up period specified by the protocol, or prescribed in clinical practice, from overdose (whether accidental or intentional), from abuse and from withdrawal.

Adverse events may also occur in screened subjects during any pre-allocation baseline period as a result of a protocol-specified intervention, including washout or discontinuation of usual therapy, diet, placebo treatment or a procedure.

All adverse events will be collected from the time the consent form is signed through 14 days (42 days for live attenuated vaccines) following the first vaccination(s) and from the time of any subsequent vaccination(s) through 14 days (42 days for live attenuated vaccines) thereafter, and such events will be recorded at each examination on the Adverse Event case report forms/worksheets.

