### **8.2.3.3 Safety Endpoints**

Safety assessment will focus on the injection site adverse experiences/vaccine-related adverse experiences prompted for on the VRC occurring Day 1 through Day 5 following any vaccination, elevated temperature from Day 1 to 5 following any vaccination and systemic adverse experiences/vaccine-related adverse experiences occurring Day 1 through Day 15 following any vaccination. Serious adverse experiences occurring Day 1 through Day 15 following any vaccination, serious vaccine-related adverse experiences and new medical condition occurring any time during the study will be summarized.

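### Outside the 14-day post-vaccination windows, a serious non-fatal event caused by a study procedure need not be reported as an SAE, although the protocol counts such events as adverse events

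*Combined protocol and SAP*

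**What the plan says.** **Definition.** Section 7.2 treats an event as adverse if it is associated in time with a medicinal product or with a procedure that the protocol specifies. It adds that the Sponsor's "product includes any pharmaceutical product, biological product, device, diagnostic agent or protocol-specified procedure". The SAE definition in Section 7.2.2.1 is built on the same term.

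**Inside the windows.** Section 7.2 states: "All adverse events will be collected from the time the consent form is signed through 14 days" after the first vaccination, and then from each later vaccination to 14 days after it. Under Section 7.2.2.1 any SAE in those periods, "whether or not related to the Sponsor's product, must be reported within 24 hours to the" Sponsor.

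**Outside the windows.** Section 7.2.2.1 leaves two triggers: "A death that resulted in the subject discontinuing the trial", and "A serious adverse event that is considered by an investigator who is a qualified physician to be vaccine related". Section 4.2.3.3, item 3, has the same scope for the study as a whole.

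**Procedures.** The flow chart (Section 6.0) schedules file and swab sampling at Day 1 and Months 7, 12, 18, 24, 30 and 36, and allows lesion biopsy, if indicated, at every visit from Month 2. The Month 7 visit is due "3 to 7 weeks after Month 6". Section 7.1.3.3 states: "Management of anogenital warts is a study procedure".

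**Analysis.** Section 8.2.3.3 states: "serious vaccine-related adverse experiences and new medical condition occurring any time during the study will be summarized".

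**The concern.** The definition of an adverse event includes procedures. The reporting rule outside the windows does not. If a man is admitted to hospital at Month 18 with bleeding or infection after a study biopsy, the event meets the protocol's own definition of an SAE. If the physician judges that the vaccine did not cause it, neither trigger applies. No 24-hour report is then required, and Table 2 asks about causality for the test vaccine only.

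What is at stake is safety oversight of healthy volunteers, some of them minors, during the part of the study in which most of the procedures take place. Procedure-related SAEs would not be identifiable as such in the SAE data.

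**Working it through.** The plan gives no figure on this point, so there is none to reproduce. The check compares the passages and then counts days.

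**1. Does any other passage make the event reportable?**

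- *Events of clinical interest (Section 7.2.2.2).* The only listed event is an overdose without symptoms or abnormal laboratory results.
- *Causality (Table 2, Section 7.2.3).* The relationship question concerns the test vaccine. There is no procedure item.
- *Flow chart, adverse events monitoring row.* It is marked at every visit, but Sections 7.2 and 7.2.2.1 determine what is collected and reported.
- *Medical history (Section 7.1.1.4).* New conditions after Visit 1 are collected. No step decides whether one is an SAE or was caused by a procedure.
- *Report card review (Section 7.1.2.3).* The SAE decision for conditions found at this review is made under Section 7.2.2.1, so the same triggers apply. The flow chart ends this review at Month 7.
- *Safety endpoints (Section 8.2.3.3).* New conditions at any time are summarised. Outside the windows, serious events are summarised as such only if vaccine-related.

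None of these closes the gap for a serious, non-fatal event attributed only to a procedure.

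**2. How much of the schedule lies outside the windows?**

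Inputs: doses at Day 1, Month 2 and Month 6; 30-day months and 7-day weeks (flow chart, footnote 1); Day 1 counted as day 0, so doses fall at days 0, 60 and 180.

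- Days covered at nominal dosing: 3 × 15 = 45 of 36 × 30 + 1 = 1,081, or 4.2%.
- Month 7: 3 × 7 = 21 to 7 × 7 = 49 days after Month 6. The earliest on-schedule visit, at 21 days, is past day 14.
- Month 12: earliest day 360 − 28 = 332. The latest on-schedule end of the third window is 180 + 28 + 14 = day 222. Months 12 to 36 are all outside.
- Swab visits outside: 6 of 7. With 4 specimens per visit (penile, scrotal, perineal/perianal, intra-anal), 6 × 4 = 24 of 7 × 4 = 28 specimens per man.
- Visits at which biopsy is allowed: 8, of which 6 (Months 7 to 36) are outside. The Month 2 and Month 6 visits coincide with a dose.

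**3. How many sampling visits is that?**

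- Without attrition: 1,100 × 6 = 6,600.
- With the completion figures in Section 8.2.7: 1,100 × 0.90 = 990 men at Month 7 and 990 × 0.80 = 792 at Month 36. Assuming linear loss, the mean is (990 + 792)/2 = 891, and 891 × 6 = 5,346.

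These are counts of visits, not of harms. The documents give neither the expected number of biopsies nor a rate of serious procedure events.

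**The case against.** The strongest defence is that the scope is deliberate. Sections 4.2.3.3, 7.2.2.1 and 8.2.3.3 agree with one another: all SAEs near vaccination, then deaths and vaccine-related SAEs. Defining an adverse event does not promise to collect every such event for 36 months. Most of the visits counted above involve surface filing and swabbing; biopsy is done only if indicated, and the choice of wart treatment follows site practice. This limits how much harm can be expected. It does not explain why events that Section 7.2 expressly includes are then left out of reporting.

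A reader might infer several stronger conclusions that the documents do not support:

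- *That such harm leaves no record.* Adverse event monitoring and medical history updates are marked at every visit after Day 1, and new conditions are summarised. What is missing is the required SAE report and the procedure-causality assessment.
- *That no follow-up to outcome is required.* Section 7.2.2.1 requires it for all subjects with SAEs, without limiting this to reportable ones.
- *That the report card rule governs a Month 18 event.* It applies only at report card review, through Month 7.
- *That the DMC and sponsor could not see the event at all.* New conditions are study data, and the DMC charter and eCRF guidelines, which are not in these documents, may ask for more.
- *That the tolerability conclusion is compromised.* The second primary objective (Section 3.1) concerns the 3-dose vaccine regimen. Harm due only to a later biopsy does not bear on it, and a serious event judged vaccine-related is reportable at any time.

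**Conclusion.** The gap is real but narrow. As written, a serious, non-fatal event attributed to study sampling, biopsy or study treatment of a lesion at Months 7 to 36 need not be reported to the sponsor as an SAE. It has no procedure-causality assessment and can be captured only as a new medical condition. This applies to 6 of the 7 scheduled swab visits and to biopsies at 6 of the 8 visits that allow them, assuming visits take place within the flow chart windows.

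Three situations are covered: fatal complications at any time, through the death trigger; Day 1 sampling, because the first window opens at consent; and biopsy events within 14 days after the Month 2 or Month 6 dose. The number of serious events that would be missed cannot be estimated from the documents and may be small. Efficacy, alpha, power and the vaccine-tolerability objective are unaffected. The change is still worth making, because it costs little and brings the reporting rule into line with the protocol's own definition.

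**What to change.** Reconcile Section 7.2 with Section 7.2.2.1:

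1. In Section 7.2.2.1, extend the second out-of-window trigger to SAEs that the same physician considers related to the study vaccine or to a protocol-specified procedure. Name file and swab sampling, biopsy and study treatment of lesions.
2. Make the same change in Section 4.2.3.3, item 3.
3. In Section 8.2.3.3, summarise procedure-related SAEs at any time during the study, alongside serious vaccine-related events.
4. In Table 2 and the eCRF, add a yes/no item on relationship to a study procedure next to the vaccine-causality item.

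The cost is protocol wording, one eCRF field and a few extra SAE reports. No new visit, procedure or staff is needed, and clinical management does not change.

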### **7.2.2.2 Events of Clinical Interest**

Selected non-serious and serious adverse events are also known as Events of Clinical Interest (ECI) and must be recorded as such on the Adverse Event case report forms/worksheets and reported within 24 hours to the Sponsor either by electronic media or paper. Sponsor Contact information can be found in the Investigator Trial File Binder.

Events of clinical interest for this trial include:

- an overdose of Sponsor's product, as defined in Section 7.2.1 - Definition of an Overdose for This Protocol and Reporting of Overdose to the Sponsor, that is not associated with clinical symptoms or abnormal laboratory results.

### **7.2.3 Evaluating Adverse Events**

An investigator who is a qualified physician will evaluate all adverse events with respect to the elements outlined in Table 2. The investigator's assessment of causality is required for each adverse event. Refer to [Table 2](#) for instructions in evaluating adverse events.

Table 2 Evaluating Adverse Events

Maximum Intensity	Mild	awareness of sign or symptom, but easily tolerated (for pediatric trials, awareness of symptom, but easily tolerated)
	Moderate	discomfort enough to cause interference with usual activity (for pediatric trials, definitely acting like something is wrong)
	Severe	incapacitating with inability to work or do usual activity (for pediatric trials, extremely distressed or unable to do usual activities) Injection site redness or swelling from the day of vaccination through Day 4 post-vaccination will be evaluated by maximum size.
Seriousness	A serious adverse event (AE) is any adverse event occurring at any dose that:	
	† Results in death; or	
	† Is life threatening; or places the subject, in the view of the investigator, at immediate risk of death from the event as it occurred [Note: This does not include an adverse event that, had it occurred in a more severe form, might have caused death.]; or	
	† Results in a persistent or significant disability/incapacity (substantial disruption of one’s ability to conduct normal life functions); or	
	† Results in or prolongs an existing inpatient hospitalization (hospitalization is defined as an inpatient admission, regardless of length of stay, even if the hospitalization is a precautionary measure for continued observation. (Note: Hospitalization [including hospitalization for an elective procedure] for a preexisting condition which has not worsened does not constitute a serious adverse event.); or	
	† Is a congenital anomaly/birth defect (in offspring of subject taking the product regardless of time to diagnosis); or	
	Is a cancer; or	
Duration	Is associated with an overdose (whether accidental or intentional). Any adverse event associated with an overdose is considered a serious adverse event. An overdose that is not associated with an adverse event is considered a non-serious event of clinical interest and must be reported within 24 hours.	
	Other important medical events that may not result in death, not be life threatening, or not require hospitalization may be considered a serious adverse event when, based upon appropriate medical judgment, the event may jeopardize the subject and may require medical or surgical intervention to prevent one of the outcomes listed previously (designated above by a †).	
	Record the start and stop dates of the adverse event. If less than 1 day, indicate the appropriate length of time and units	
Action taken	Did the adverse event cause the test vaccine to be discontinued?	
Relationship to test vaccine	Did the test vaccine cause the adverse event? The determination of the likelihood that the test vaccine caused the adverse event will be provided by an investigator who is a qualified physician. The investigator’s signed/dated initials on the source document or worksheet that supports the causality noted on the AE form, ensures that a medically qualified assessment of causality was done. This initialed document must be retained for the required regulatory time frame. The criteria below are intended as reference guidelines to assist the investigator in assessing the likelihood of a relationship between the test vaccine and the adverse event based upon the available information. The following components are to be used to assess the relationship between the test vaccine and the AE; the greater the correlation with the components and their respective elements (in number and/or intensity), the more likely the test vaccine caused the adverse event:	
	Exposure	Is there evidence that the subject was actually exposed to the test vaccine such as: reliable history, acceptable compliance assessment (e.g., diary), seroconversion or identification of vaccine virus in bodily specimen?
	Time Course	Did the AE follow in a reasonable temporal sequence from administration of the test vaccine? Is the time of onset of the AE compatible with a vaccine-induced effect?
	Likely Cause	Is the AE not reasonably explained by another etiology such as underlying disease, other drug(s)/vaccine(s), or other host or environmental factors

Relationship to test vaccine (continued)	The following components are to be used to assess the relationship between the test vaccine and the AE: (continued)	
	Dechallenge	(not applicable for vaccines)
	Rechallenge	
Was the subject reexposed to the test vaccine in this trial?          If yes, did the AE recur or worsen?          If yes, this is a positive rechallenge. If no, this is a negative rechallenge.          (Note: This criterion is not applicable if: (1) the initial AE resulted in death or permanent disability, or (2) the trial is a single-dose vaccine trial.)          NOTE: IF A RECHALLENGE IS PLANNED FOR AN ADVERSE EVENT WHICH WAS SERIOUS AND WHICH MAY HAVE BEEN CAUSED BY THE TEST VACCINE, OR IF REEXPOSURE TO THE TEST VACCINE POSES ADDITIONAL POTENTIAL SIGNIFICANT RISK TO THE SUBJECT, THEN THE RECHALLENGE MUST BE APPROVED IN ADVANCE BY THE U.S. CLINICAL MONITOR AND THE INSTITUTIONAL REVIEW BOARD/INDEPENDENT ETHICS COMMITTEE.

Consistency with Trial Vaccine Profile	Is the clinical/pathological presentation of the AE consistent with previous knowledge regarding the test vaccine or vaccine class pharmacology or toxicology?	
The assessment of relationship will be reported on the case report forms /worksheets by an investigator who is a qualified physician according to his/her best clinical judgment, including consideration of the above elements.		
Record one of the following:	Use the following criteria as guidance (not all criteria must be present to be indicative of a vaccine relationship).	
Yes, there is a reasonable possibility of vaccine relationship.	There is evidence of exposure to the test vaccine. The temporal sequence of the AE onset relative to the administration of the test vaccine is reasonable. The AE is more likely explained by the test vaccine than by another cause.	
No, there is not a reasonable possibility of vaccine relationship	Subject did not receive the test vaccine OR temporal sequence of the AE onset relative to administration of the test vaccine is not reasonable OR there is another obvious cause of the AE. (Also entered for a subject with overdose without an associated AE.)	

